Injection Site Erythema or Redness¹² Report only one > 15 years of age	2.5 to < 5 cm in diameter OR 6.25 to < 25 cm ² surface area AND Symptoms causing no or minimal interference with usual social & functional activities	≥ 5 to < 10 cm in diameter OR ≥ 25 to < 100 cm ² surface area OR Symptoms causing greater than minimal interference with usual social & functional activities	≥ 10 cm in diameter OR ≥ 100 cm ² surface area OR Ulceration OR Secondary infection OR Phlebitis OR Sterile abscess OR Drainage OR Symptoms causing inability to perform usual social & functional activities	Potentially life-threatening consequences (e.g., abscess, exfoliative dermatitis, necrosis involving dermis or deeper tissue)
≤ 15 years of age	≤ 2.5 cm in diameter	> 2.5 cm in diameter with < 50% surface area of the extremity segment involved (e.g., upper arm or thigh)	≥ 50% surface area of the extremity segment involved (e.g., upper arm or thigh) OR Ulceration OR Secondary infection OR Phlebitis OR Sterile abscess OR Drainage	Potentially life-threatening consequences (e.g., abscess, exfoliative dermatitis, necrosis involving dermis or deeper tissue)
Injection Site Induration or Swelling Report only one > 15 years of age	Same as for Injection Site Erythema or Redness , > 15 years of age	Same as for Injection Site Erythema or Redness , > 15 years of age	Same as for Injection Site Erythema or Redness , > 15 years of age	Same as for Injection Site Erythema or Redness , > 15 years of age
≤ 15 years of age	Same as for Injection Site Erythema or Redness , ≤ 15 years of age	Same as for Injection Site Erythema or Redness , ≤ 15 years of age	Same as for Injection Site Erythema or Redness , ≤ 15 years of age	Same as for Injection Site Erythema or Redness , ≤ 15 years of age
Injection Site Pruritus	Itching localized to the injection site that is relieved spontaneously or in < 48 hours of treatment	Itching beyond the injection site that is not generalized OR Itching localized to the injection site requiring ≥ 48 hours treatment	Generalized itching causing inability to perform usual social & functional activities	NA

¹² Injection Site Erythema or Redness should be evaluated and graded using the greatest single diameter or measured surface area.

Laboratory Values*

Chemistries

PARAMETER	GRADE 1 MILD	GRADE 2 MODERATE	GRADE 3 SEVERE	GRADE 4 POTENTIALLY LIFE- THREATENING
Acidosis	NA	pH \geq 7.3 to $<$ LLN	pH $<$ 7.3 without life-threatening consequences	pH $<$ 7.3 with life-threatening consequences
Albumin, Low (g/dL; g/L)	3.0 to $<$ LLN 30 to $<$ LLN	\geq 2.0 to $<$ 3.0 \geq 20 to $<$ 30	$<$ 2.0 $<$ 20	NA
Alkaline Phosphatase, High	1.25 to $<$ 2.5 x ULN	2.5 to $<$ 5.0 x ULN	5.0 to $<$ 10.0 x ULN	\geq 10.0 x ULN
Alkalosis	NA	pH $>$ ULN to \leq 7.5	pH $>$ 7.5 without life-threatening consequences	pH $>$ 7.5 with life-threatening consequences
ALT or SGPT, High Report only one	1.25 to $<$ 2.5 x ULN	2.5 to $<$ 5.0 x ULN	5.0 to $<$ 10.0 x ULN	\geq 10.0 x ULN
Amylase (Pancreatic) or Amylase (Total), High Report only one	1.1 to $<$ 1.5 x ULN	1.5 to $<$ 3.0 x ULN	3.0 to $<$ 5.0 x ULN	\geq 5.0 x ULN
AST or SGOT, High Report only one	1.25 to $<$ 2.5 x ULN	2.5 to $<$ 5.0 x ULN	5.0 to $<$ 10.0 x ULN	\geq 10.0 x ULN
Bicarbonate, Low (mEq/L; mmol/L)	16.0 to $<$ LLN 16.0 to $<$ LLN	11.0 to $<$ 16.0 11.0 to $<$ 16.0	8.0 to $<$ 11.0 8.0 to $<$ 11.0	$<$ 8.0 $<$ 8.0
Bilirubin Direct Bilirubin¹³, High > 28 days of age	NA	NA	$>$ ULN with other signs and symptoms of hepatotoxicity.	$>$ ULN with life-threatening consequences (e.g., signs and symptoms of liver failure)
\leq 28 days of age	ULN to \leq 1 mg/dL	$>$ 1 to \leq 1.5 mg/dL	$>$ 1.5 to \leq 2 mg/dL	$>$ 2 mg/dL
Total Bilirubin, High > 28 days of age	1.1 to $<$ 1.6 x ULN	1.6 to $<$ 2.6 x ULN	2.6 to $<$ 5.0 x ULN with other signs and symptoms of hepatotoxicity.	\geq 5.0 x ULN with life-threatening consequences (e.g., signs and symptoms of liver failure).
\leq 28 days of age	See Appendix A. Total Bilirubin for Term and Preterm Neonates	See Appendix A. Total Bilirubin for Term and Preterm Neonates	See Appendix A. Total Bilirubin for Term and Preterm Neonates	See Appendix A. Total Bilirubin for Term and Preterm Neonates

*Reminder: An asymptomatic abnormal laboratory finding without an accompanying AE should not be reported to DAIDS in an expedited time frame unless it meets protocol-specific reporting requirements.

¹³ Direct bilirubin $>$ 1.5 mg/dL in a participant $<$ 28 days of age should be graded as grade 2, if $<$ 10% of the total bilirubin.

Chemistries

PARAMETER	GRADE 1 MILD	GRADE 2 MODERATE	GRADE 3 SEVERE	GRADE 4 POTENTIALLY LIFE- THREATENING
Calcium, High (mg/dL; mmol/L) ≥ 7 days of age	10.6 to < 11.5 2.65 to < 2.88	11.5 to < 12.5 2.88 to < 3.13	12.5 to < 13.5 3.13 to < 3.38	≥ 13.5 ≥ 3.38
< 7 days of age	11.5 to < 12.4 2.88 to < 3.10	12.4 to < 12.9 3.10 to < 3.23	12.9 to < 13.5 3.23 to < 3.38	≥ 13.5 ≥ 3.38
Calcium (Ionized), High (mg/dL; mmol/L)	> ULN to < 6.0 > ULN to < 1.5	6.0 to < 6.4 1.5 to < 1.6	6.4 to < 7.2 1.6 to < 1.8	≥ 7.2 ≥ 1.8
Calcium, Low (mg/dL; mmol/L) ≥ 7 days of age	7.8 to < 8.4 1.95 to < 2.10	7.0 to < 7.8 1.75 to < 1.95	6.1 to < 7.0 1.53 to < 1.75	< 6.1 < 1.53
< 7 days of age	6.5 to < 7.5 1.63 to < 1.88	6.0 to < 6.5 1.50 to < 1.63	5.50 to < 6.0 1.38 to < 1.50	< 5.50 < 1.38
Calcium (Ionized), Low (mg/dL; mmol/L)	< LLN to 4.0 < LLN to 1.0	3.6 to < 4.0 0.9 to < 1.0	3.2 to < 3.6 0.8 to < 0.9	< 3.2 < 0.8
Cardiac Troponin I, High	NA	NA	NA	Levels consistent with myocardial infarction or unstable angina as defined by the local laboratory
Creatine Kinase, High	3 to < 6 x ULN	6 to < 10x ULN	10 to < 20 x ULN	≥ 20 x ULN
Creatinine, High *Report only one	1.1 to 1.3 x ULN	> 1.3 to 1.8 x ULN OR Increase to 1.3 to < 1.5 x participant's baseline	> 1.8 to < 3.5 x ULN OR Increase to 1.5 to < 2.0 x participant's baseline	≥ 3.5 x ULN OR Increase of ≥ 2.0 x participant's baseline
Creatinine Clearance¹⁴ or eGFR, Low *Report only one	NA	< 90 to 60 ml/min or ml/min/1.73 m ² OR 10 to < 30% decrease from participant's baseline	< 60 to 30 ml/min or ml/min/1.73 m ² OR 30 to < 50% decrease from participant's baseline	< 30 ml/min or ml/min/1.73 m ² OR ≥ 50% decrease from participant's baseline or dialysis needed
Glucose (mg/dL; mmol/L) Fasting, High	110 to 125 6.11 to < 6.95	> 125 to 250 6.95 to < 13.89	> 250 to 500 13.89 to < 27.75	≥ 500 ≥ 27.75
Nonfasting, High	116 to 160 6.44 to < 8.89	> 160 to 250 8.89 to < 13.89	> 250 to 500 13.89 to < 27.75	≥ 500 ≥ 27.75

¹⁴ Use the applicable formula (i.e., Cockcroft-Gault in mL/min or Schwartz, MDRD, CKD-Epi in mL/min/1.73m²). Sites should choose the method defined in their study and when not specified, use the method most relevant to the study population.

*Reminder: Choose the method that selects for the higher grade.

Chemistries

PARAMETER	GRADE 1 MILD	GRADE 2 MODERATE	GRADE 3 SEVERE	GRADE 4 POTENTIALLY LIFE- THREATENING
Glucose, Low (mg/dL; mmol/L) ≥ 1 month of age	55 to 64 3.05 to <3.55	40 to <55 2.22 to < 3.05	30 to <40 1.67 to < 2.22	<30 < 1.67
< 1 month of age	50 to 54 2.78 to < 3.00	40 to <50 2.22 to < 2.78	30 to <40 1.67 to < 2.22	<30 < 1.67
Lactate, High	ULN to < 2.0 x ULN without acidosis	≥ 2.0 x ULN without acidosis	Increased lactate with pH < 7.3 without life- threatening consequences	Increased lactate with pH < 7.3 with life- threatening consequences
Lipase, High	1.1 to < 1.5 x ULN	1.5 to < 3.0 x ULN	3.0 to < 5.0 x ULN	≥ 5.0 x ULN
Lipid Disorders (mg/dL; mmol/L)				
Cholesterol, Fasting, High ≥ 18 years of age	200 to < 240 5.18 to < 6.19	240 to < 300 6.19 to < 7.77	≥ 300 ≥ 7.77	NA
< 18 years of age	170 to < 200 4.40 to < 5.15	200 to < 300 5.15 to < 7.77	≥ 300 ≥ 7.77	NA
LDL, Fasting, High ≥ 18 years of age	130 to < 160 3.37 to < 4.12	160 to < 190 4.12 to < 4.90	≥ 190 ≥ 4.90	NA
> 2 to < 18 years of age	110 to < 130 2.85 to < 3.34	130 to < 190 3.34 to < 4.90	≥ 190 ≥ 4.90	NA
Triglycerides, Fasting, High	150 to 300 1.71 to 3.42	>300 to 500 >3.42 to 5.7	>500 to < 1,000 >5.7 to 11.4	> 1,000 > 11.4
Magnesium¹⁵, Low (mEq/L; mmol/L)	1.2 to < 1.4 0.60 to < 0.70	0.9 to < 1.2 0.45 to < 0.60	0.6 to < 0.9 0.30 to < 0.45	< 0.6 < 0.30
Phosphate, Low (mg/dL; mmol/L) > 14 years of age	2.0 to < LLN 0.65 to < LLN	1.4 to < 2.0 0.45 to < 0.65	1.0 to < 1.4 0.32 to < 0.45	< 1.0 < 0.32
1 to 14 years of age	3.0 to < 3.5 0.97 to < 1.13	2.5 to < 3.0 0.81 to < 0.97	1.5 to < 2.5 0.48 to < 0.81	< 1.5 < 0.48
< 1 year of age	3.5 to < 4.5 1.13 to < 1.45	2.5 to < 3.5 0.81 to < 1.13	1.5 to < 2.5 0.48 to < 0.81	< 1.5 < 0.48
Potassium, High (mEq/L; mmol/L)	5.6 to < 6.0 5.6 to < 6.0	6.0 to < 6.5 6.0 to < 6.5	6.5 to < 7.0 6.5 to < 7.0	≥ 7.0 ≥ 7.0
Potassium, Low (mEq/L; mmol/L)	3.0 to < 3.4 3.0 to < 3.4	2.5 to < 3.0 2.5 to < 3.0	2.0 to < 2.5 2.0 to < 2.5	< 2.0 < 2.0

¹⁵ To convert a magnesium value from mg/dL to mmol/L, laboratories should multiply by 0.4114.

Chemistries

PARAMETER	GRADE 1 MILD	GRADE 2 MODERATE	GRADE 3 SEVERE	GRADE 4 POTENTIALLY LIFE- THREATENING
Sodium, High (mEq/L; mmol/L)	146 to < 150 146 to < 150	150 to < 154 150 to < 154	154 to < 160 154 to < 160	≥ 160 ≥ 160
Sodium, Low (mEq/L; mmol/L)	130 to < 135 130 to < 135	125 to < 130 125 to < 130	121 to < 125 121 to < 125	≤ 120 ≤ 120
Uric Acid, High (mg/dL; mmol/L)	7.5 to < 10.0 0.45 to < 0.59	10.0 to < 12.0 0.59 to < 0.71	12.0 to < 15.0 0.71 to < 0.89	≥ 15.0 ≥ 0.89

Hematology

PARAMETER	GRADE 1 MILD	GRADE 2 MODERATE	GRADE 3 SEVERE	GRADE 4 POTENTIALLY LIFE- THREATENING
Absolute CD4+ Count, Low (cell/mm ³ ; cells/L) > 5 years of age (not HIV infected)	300 to < 400 300 to < 400	200 to < 300 200 to < 300	100 to < 200 100 to < 200	< 100 < 100
Absolute Lymphocyte Count, Low (cell/mm ³ ; cells/L) > 5 years of age (not HIV infected)	600 to < 650 0.600 x 10 ⁹ to < 0.650 x 10 ⁹	500 to < 600 0.500 x 10 ⁹ to < 0.600 x 10 ⁹	350 to < 500 0.350 x 10 ⁹ to < 0.500 x 10 ⁹	< 350 < 0.350 x 10 ⁹
Absolute Neutrophil Count (ANC), Low (cells/mm ³ ; cells/L) > 7 days of age	800 to 1,000 0.800 x 10 ⁹ to 1.000 x 10 ⁹	600 to 799 0.600 x 10 ⁹ to 0.799 x 10 ⁹	400 to 599 0.400 x 10 ⁹ to 0.599 x 10 ⁹	< 400 < 0.400 x 10 ⁹
2 to 7 days of age	1,250 to 1,500 1.250 x 10 ⁹ to 1.500 x 10 ⁹	1,000 to 1,249 1.000 x 10 ⁹ to 1.249 x 10 ⁹	750 to 999 0.750 x 10 ⁹ to 0.999 x 10 ⁹	< 750 < 0.750 x 10 ⁹
≤ 1 day of age	4,000 to 5,000 4.000 x 10 ⁹ to 5.000 x 10 ⁹	3,000 to 3,999 3.000 x 10 ⁹ to 3.999 x 10 ⁹	1,500 to 2,999 1.500 x 10 ⁹ to 2.999 x 10 ⁹	< 1,500 < 1.500 x 10 ⁹
Fibrinogen, Decreased (mg/dL; g/L)	100 to < 200 1.00 to < 2.00 OR 0.75 to < 1.00 x LLN	75 to < 100 0.75 to < 1.00 OR ≥ 0.50 to < 0.75 x LLN	50 to < 75 0.50 to < 0.75 OR 0.25 to < 0.50 x LLN	< 50 < 0.50 OR < 0.25 x LLN OR Associated with gross bleeding
Hemoglobin¹⁶, Low (g/dL; mmol/L) ¹⁷ ≥ 13 years of age (male only)	10.0 to 10.9 6.19 to 6.76	9.0 to < 10.0 5.57 to < 6.19	7.0 to < 9.0 4.34 to < 5.57	< 7.0 < 4.34
≥ 13 years of age (female only)	9.5 to 10.4 5.88 to 6.48	8.5 to < 9.5 5.25 to < 5.88	6.5 to < 8.5 4.03 to < 5.25	< 6.5 < 4.03

¹⁶ Male and female sex are defined as sex at birth. For transgender participants ≥13 years of age who have been on hormone therapy for more than 6 consecutive months, grade hemoglobin based on the gender with which they identify (i.e., a transgender female should be graded using the female sex at birth hemoglobin laboratory values).

¹⁷ The most commonly used conversion factor to convert g/dL to mmol/L is 0.6206. For grading hemoglobin results obtained by an analytic method with a conversion factor other than 0.6206, the result must be converted to g/dL using appropriate conversion factor for the particular laboratory.

Hematology

PARAMETER	GRADE 1 MILD	GRADE 2 MODERATE	GRADE 3 SEVERE	GRADE 4 POTENTIALLY LIFE- THREATENING
57 days of age to < 13 years of age (male and female)	9.5 to 10.4 5.88 to 6.48	8.5 to < 9.5 5.25 to < 5.88	6.5 to < 8.5 4.03 to < 5.25	< 6.5 < 4.03
36 to 56 days of age (male and female)	8.5 to 9.6 5.26 to 5.99	7.0 to < 8.5 4.32 to < 5.26	6.0 to < 7.0 3.72 to < 4.32	< 6.0 < 3.72
22 to 35 days of age (male and female)	9.5 to 11.0 5.88 to 6.86	8.0 to < 9.5 4.94 to < 5.88	6.7 to < 8.0 4.15 to < 4.94	< 6.7 < 4.15
8 to ≤ 21 days of age (male and female)	11.0 to 13.0 6.81 to 8.10	9.0 to < 11.0 5.57 to < 6.81	8.0 to < 9.0 4.96 to < 5.57	< 8.0 < 4.96
≤ 7 days of age (male and female)	13.0 to 14.0 8.05 to 8.72	10.0 to < 13.0 6.19 to < 8.05	9.0 to < 10.0 5.59 to < 6.19	< 9.0 < 5.59
INR, High (not on anticoagulation therapy)	1.1 to < 1.5 x ULN	1.5 to < 2.0 x ULN	2.0 to < 3.0 x ULN	≥ 3.0 x ULN
Methemoglobin (% hemoglobin)	5.0 to < 10.0%	10.0 to < 15.0%	15.0 to < 20.0%	≥ 20.0%
PTT, High (not on anticoagulation therapy)	1.1 to < 1.66 x ULN	1.66 to < 2.33 x ULN	2.33 to < 3.00 x ULN	≥ 3.00 x ULN
Platelets, Decreased (cells/mm ³ ; cells/L)	100,000 to < 125,000 100.000×10^9 to < 125.000×10^9	50,000 to < 100,000 50.000×10^9 to < 100.000×10^9	25,000 to < 50,000 25.000×10^9 to < 50.000×10^9	< 25,000 < 25.000×10^9
PT, High (not on anticoagulation therapy)	1.1 to < 1.25 x ULN	1.25 to < 1.50 x ULN	1.50 to < 3.00 x ULN	≥ 3.00 x ULN
WBC, Decreased (cells/mm ³ ; cells/L)				
> 7 days of age	2,000 to 2,499 2.000×10^9 to 2.499×10^9	1,500 to 1,999 1.500×10^9 to 1.999×10^9	1,000 to 1,499 1.000×10^9 to 1.499×10^9	< 1,000 < 1.000×10^9
≤ 7 days of age	5,500 to 6,999 5.500×10^9 to 6.999×10^9	4,000 to 5,499 4.000×10^9 to 5.499×10^9	2,500 to 3,999 2.500×10^9 to 3.999×10^9	< 2,500 < 2.500×10^9

Urinalysis

PARAMETER	GRADE 1 MILD	GRADE 2 MODERATE	GRADE 3 SEVERE	GRADE 4 POTENTIALLY LIFE- THREATENING
Glycosuria (random collection tested by dipstick)	Trace to 1+ or ≤ 250 mg	2+ or > 250 to ≤ 500 mg	> 2+ or > 500 mg	NA
Hematuria (not to be reported based on dipstick findings or on blood believed to be of menstrual origin)	6 to < 10 RBCs per high power field	≥ 10 RBCs per high power field	Gross, with or without clots OR With RBC casts OR Intervention indicated	Life-threatening consequences
Proteinuria (random collection tested by dipstick)	1+	2+	3+ or higher	NA

Reference

U.S. Department of Health and Human Services, National Institutes of Health, National Institute of Allergy and Infectious Diseases, Division of AIDS. Division of AIDS (DAIDS) Table for Grading the Severity of Adult and Pediatric Adverse Events, Version 2.1. [March 2017]. Available from:

<https://rsc.tech-res.com/docs/default-source/safety/daids-ae-grading-table-mar2017.pdf>

11.3. Appendix 3: Liver Safety – Study Treatment Restart or Rechallenge Guidelines

11.3.1. VSLC Guidelines for Drug Restart or Rechallenge after stop for Liver criteria

Drug Rechallenge refers to resuming study treatment following drug induced liver injury (DILI). Because of the risks associated with rechallenge after DILI (see Drug Rechallenge Background below) this should only be considered for a participant for whom there is compelling evidence of benefit from a critical or life-saving medicine, there is no alternative approved medicine available, and a benefit:risk assessment of rechallenge is considered to be favorable (Table 12, Figure 17).

Drug Restart refers to resuming study treatment following liver events meeting stopping criteria **in which there is a clear underlying cause (other than DILI) of the liver event (e.g., biliary obstruction, pancreatic events, hypotension, acute viral hepatitis)**. Furthermore, there should be no evidence of alcoholic hepatitis or hypersensitivity, and the drug should not be associated with HLA markers of liver injury. (Table 13; Figure 18).

As this determination can be difficult, for the purpose of these guidelines, cases should be treated as rechallenges if there is any reasonable likelihood that the liver event is related to study drug. Restarts should be limited to cases in which there is clear evidence that the underlying cause of the liver event is not related to study drug.

DRUG RECHALLENGE

Background: Following drug-induced liver injury, drug rechallenge is associated with a 13% mortality across all drugs in prospective studies [Andrade, 2009]. Clinical outcomes vary by drug, with nearly 50% fatality with halothane re-administered within one month of initial injury. However, some drugs seldom result in recurrent liver injury or fatality.

Risk factors for a fatal drug rechallenge outcome include:

[figure not shown]
- hypersensitivity [Andrade, 2009] with initial liver injury (e.g. fever, rash, eosinophilia)
- jaundice or bilirubin >2xULN with initial liver injury (direct bilirubin >35% of total)
- participant currently exhibits severe liver injury defined by: ALT≥3xULN, bilirubin ≥2xULN (direct bilirubin >35% of total), or INR≥1.5
- prior serious adverse event or fatality has earlier been observed with drug rechallenge [Papay, 2009; Hunt, 2010]
- evidence of drug-related nonclinical liability (e.g. reactive metabolites; mitochondrial impairment [Hunt, 2010])

11.3.2. VSLC Decision Process for Drug Rechallenge Approval or Disapproval

- Principal Investigator (PI) requests consideration of drug rechallenge for a participant receiving compelling benefit from a critical or life-saving drug, who exhibits liver chemistry elevation meeting participant stopping criteria in relation to DILI, with no alternative treatment
- By definition treatment naïve participants will only be considered for rechallenge if they were infected with a multi-resistant virus.
- Medical Monitor and Global Clinical Safety and Pharmacovigilance (GCSP) Physician review the participant's rechallenge risk factors (consultation with the Hepatotoxicity Panel is available) and complete checklist (Table 12).
- The local operating company (LOC) medical directors (ViiV and/or GSK where applicable) should be informed that study drug rechallenge is under consideration and of the final decision, whether or not to proceed.
- The Medical Monitor and GCSP Physician are accountable to review and agree on the following prior to preparing request for rechallenge documentation for presentation to VSLC:
 - Compelling benefit of the investigational product (IP) for this participant and no alternative therapy
 - *must present source data defining the patient's current resistance profile with documented evidence of extensive drug resistance and previous drug history*
- Relative benefit-risk of drug rechallenge, with consideration of the following high risk factors:
 - Initial liver injury event included: fever, rash, eosinophilia, or bilirubin $\geq 2xULN$ (or direct bilirubin $>35\%$ of total, if available)
 - Participant currently exhibits severe liver injury defined by: ALT $>3xULN$, bilirubin $>2xULN$ (direct bilirubin $>35\%$ of total, if available), or INR >1.5
 - SAE or fatality has earlier been observed with IP rechallenge
 - IP is associated with known nonclinical hepatic liability/ injury
- Relevant physicians (listed below) must review and agree on action to be taken regarding request for drug rechallenge:
 - Safety Review Team Leader, Safety Development Leader, or Senior Safety Physician
 - Medicines Development Leader (MDL) and Project Physician Leader (PPL)
- Request is taken to full VSLC for final decision

Table 12 Checklist for drug rechallenge for critical medicine (Following drug-induced liver injury, drug rechallenge is associated with 13% mortality across all drugs in prospective studies)

	Yes	No
Compelling benefit of IP for this participant and no alternative therapy. Provide brief explanation:		
Relative benefit-risk favorable for drug rechallenge, after considering the following high risk factors:		
Initial liver injury event included:		
fever, rash, eosinophilia, or hypersensitivity		
bilirubin \geq 2xULN (direct bilirubin >35% of total)		
Participant currently exhibits ALT >3xULN, bilirubin >2xULN (direct bilirubin >35% of total, if available), or INR>1.5		
SAE or fatality has earlier been observed with IP rechallenge If yes, please provide brief explanation:		
IP associated with known nonclinical hepatic liability/ injury		
Source data defining the patient's current resistance profile		
Previous drug history		

Figure 17 VSLC process for drug rechallenge approval or disapproval**DRUG RESTART**

“Drug restart” can be approved by the VSLC for **transient, defined non-drug-induced** liver injury if no evidence of:

- immunoallergic injury /HLA association with injury
- alcoholic hepatitis

[figure not shown]
Study drug must be held while labs and evaluation are completed to assess diagnosis.

11.3.3. VSLC Decision Process for Drug Restart Approval or Disapproval

- Principal Investigator (PI) requests consideration of drug re-initiation for a participant stable or improving on IP, who exhibits liver chemistry elevation meeting participant stopping criteria, which is transient, non-drug-related, and liver chemistries have improved to normal or are within 1.5x baseline and ALT < 5xULN.
- GSK Medical Monitor and GCSP Physician to review the participant's diagnosis restart risk factors (Hepatotoxicity Panel consultation is available) and complete checklist (Table 13).
 - *must present source data defining the patient's current resistance profile with documented evidence of extensive drug resistance and previous drug history.*
- The local operating company (LOC) medical director should be informed that study drug restart is under consideration and of the final decision, whether or not to proceed.
- Relevant physicians (listed below) must review and agree on action to be taken regarding request for drug restart:
- Safety Review Team Leader, Safety Development Leader, or Senior Safety Physician
- MDL and PPL
- Request is taken to VSLC for final decision

Table 13 Checklist for Phase III drug restart after well-explained liver injury (e.g. biliary, pancreatic, hypotensive events, congestive heart failure (CHF), acute viral hepatitis), and improvement of liver chemistry to normal or $\leq 1.5x$ baseline & ALT < 5xULN

	Yes	No
Is participant stable or improving on IP?		
Do not restart if the following risk factors at initial liver injury:		
fever, rash, eosinophilia, or hypersensitivity		
drug-induced liver injury		
alcoholic hepatitis (AST > ALT, typically < 10xULN)		
IP has an HLA genetic marker associated with liver injury (e.g. lapatinib, abacavir, amoxicillin/clavulanate)		
Source data defining the patients current resistance profile		
Previous drug history		

Figure 18 VSLC process for drug restart approval or disapproval

11.3.4. Medical monitor, GCSP Physician and PI actions for Restart or Rechallenge following VSLC decision

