5.5.1.3. Liver Chemistry Stopping Criteria – Restart / Rechallenge

Participants who meet liver toxicity stopping criteria should not be retreated with investigational product unless an exemption has been approved by the ViiV Safety and Labeling Committee (VSLC). The guideline for Restart /Rechallenge approved by the VSLC, which is maintained as a separate document must be followed.

5.5.1.3.1. Drug Restart / Rechallenge. Following Liver Events that are Possibly Related to IP

- Approval by the VSLC for drug restart or additional IM administration can be considered where:
- The participant is receiving compelling benefit, benefit of drug restart exceeds risk, and no effective alternative therapy is available. Ethics Committee or Institutional Review Board approval of drug restart / rechallenge must be obtained, as required.

- If the restart / rechallenge is approved by the VSLC in writing, the participant must be provided with a clear description of the possible benefits and risks of drug administration, including the possibility of recurrent, more severe liver injury or death.
- The participant must also provide signed informed consent specifically for the IP restart / rechallenge. Documentation of informed consent must be recorded in the study chart.
- Study drug must be administered at the dose specified by the VSLC.
- Participants approved by the VSLC for rechallenge of IP must return to the clinic twice a week for liver chemistry tests for a minimum of one month and thereafter for as long as clinically indicated and then laboratory monitoring may resume as per protocol. If protocol defined stopping criteria for liver chemistry elevations are met, study drug must be stopped.

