5.5.1.3.2. Drug Restart Following Transient Resolving Liver Events Not Related to IP

Approval by the VSLC for drug restart or additional IM administration can be considered where:

- Liver chemistries have a clear underlying cause (e.g., biliary obstruction, hypotension and liver chemistries have improved to normal or are within 1.5 x baseline and ALT <3xULN). Ethics Committee or Institutional Review Board approval of drug restart/rechallenge must be obtained, as required.
- If restart / redosing of drug is approved by the VSLC in writing, the participant must be provided with a clear description of the possible benefits and risks of drug administration, including the possibility of recurrent, more severe liver injury or death.
- The participant must also provide signed informed consent specifically for the restart. Documentation of informed consent must be recorded in the study chart.
- Study drug must be administered at the dose specified by the VSLC.

Participants approved by the VSLC for restarting or re-dosing IP must return to the clinic once a week for liver chemistry tests for a minimum of one month and thereafter for as long as clinically indicated and then laboratory monitoring may resume as per protocol. If protocol defined stopping criteria for liver chemistry elevations are met, study drug must be stopped.

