7.4.5.6. Lipase Elevations and Pancreatitis

Participants with asymptomatic Grade 1 or 2 elevations in lipase may be followed closely for the development of symptoms.

Participants with asymptomatic Grade ≥ 3 elevations in lipase that are considered possibly or probably related to IP should have IP interrupted until serum lipase returns to Grade ≤ 2 . The lipase assay should be repeated within 2 weeks of any Grade ≥ 3 result. Participants with persistence of Grade ≥ 3 lipase in the absence of other diagnoses or reoccurrence of lipase elevation (at Grade ≥ 2) following reintroduction of IP should permanently discontinue IP.

Participants with a confirmed diagnosis of clinical pancreatitis that is considered possibly or probably related to IP should have IP held. After complete resolution of the episode, participants may be re-challenged with IP after discussion with the Medical Monitor, only if the Investigator has compelling evidence that the event was not caused by IP. Upon re-challenge, lipase determinations should be performed every 2 weeks for at least 6 weeks after re-initiation of treatment. With any elevation of lipase of Grade ≥ 2 or any recurrence of symptoms, the participant should discontinue IP and be withdrawn from study.

Any participant receiving at least one dose of CAB LA and /or RPV LA who discontinue IP / Withdraw will initiate treatment with HAART and enter the LTFU Phase for 52 weeks of **follow up**.

Drug Restart Following Transient Resolving Liver Events Not Related to Study Drug

Approval by VSLC for drug restart can be considered where:

Liver chemistries have a clear underlying cause (e.g., biliary obstruction, hypotension, and liver chemistries have improved to normal or are within $1.5 \times$ baseline and $ALT < 3 \times ULN$). Ethics Committee or IRB approval of drug restart must be obtained, as required.

If restart of drug is approved by VSLC in writing, the participant must be provided with a clear description of the possible benefits and risks of drug administration, including the possibility of recurrent, more severe liver injury or death.

The participant must also provide signed informed consent specifically for the restart. Documentation of informed consent must be recorded in the study chart.

Study drug must be administered at the dose specified by VSLC.

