Participants approved by VSLC for restarting study drug must return to the clinic once a week for liver chemistry tests for a minimum of one month and thereafter for as long as clinically indicated and then laboratory monitoring may resume as per protocol. If protocol defined stopping criteria for liver chemistry elevations are met, study drug must be stopped.

Refer to Section 11.2, U.S. Department of Health and Human Services, National Institutes of Health, National Institute of Allergy and Infectious Diseases, Division of AIDS. Division of AIDS (DAIDS) Table for Grading the Severity of Adult and Pediatric Adverse Events, Version 2.1. [March 2017]. Available from: <https://rsc.tech-res.com/docs/default-source/safety/daids-ae-grading-table-mar2017.pdf>

Refer to Section 11.3, Appendix 3: Liver Safety – Study Treatment Restart Guidelines for further details.

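### The ALT limit for considering drug restart after a liver event not related to study drug is <3xULN in Sections 5.5.1.3.2 and 7.4.5.6 but <5xULN in Section 11.3.3 and Table 13

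*Protocol*

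**What the plan says.** The protocol describes restart after a liver event with a clear cause other than study drug in three sections, one of which also carries a checklist.

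- **Section 5.5.1.3.2** opens with "Approval by the VSLC for drug restart or additional IM administration can be considered where" and gives the condition as "liver chemistries have improved to normal or are within 1.5 x baseline and ALT <3xULN".
- **Section 7.4.5.6**, in restart text placed after the lipase and pancreatitis guidance, opens with "Approval by VSLC for drug restart can be considered where" and repeats the same condition, again with ALT <3xULN. It closes by sending the reader to Appendix 3: "Study Treatment Restart Guidelines for further details".
- **Section 11.3.3 (Appendix 3)** describes the request to the VSLC and gives the condition as "liver chemistries have improved to normal or are within 1.5x baseline and ALT < 5xULN".
- **Table 13**, the restart checklist in Section 11.3.3, repeats the 5xULN figure in its title: "improvement of liver chemistry to normal or $\leq 1.5x$ baseline & ALT < 5xULN".

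Section 5.5.1.3 adds: "The guideline for Restart /Rechallenge approved by the VSLC, which is maintained as a separate document must be followed". That guideline is not among the documents shown.

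**The concern.** The event type, the deciding body and the companion condition (normal, or within 1.5 times baseline) are the same throughout. Only the ALT figure changes. Rechallenge after drug-induced injury has its own rules (Sections 5.5.1.3.1 and 11.3.2), so it does not explain the difference.

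Section 5.5.1.1 forbids another injection after a liver stopping event until the VSLC approves, so this condition stands directly before redosing. A long-acting dose cannot be withdrawn: Section 2.3.1 notes that residual cabotegravir can remain for more than a year in some participants. The restart consent must mention recurrent, more severe liver injury or death. An investigator working from Section 5 and sponsor staff working from Table 13 could reach different answers on whether the same participant's case may be considered.

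**Working it through.** No sample size, power or error rate is involved. The check compares the texts and finds the ALT range in which they differ.

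**Inputs**

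- Limit A: ALT <3xULN (Sections 5.5.1.3.2 and 7.4.5.6).
- Limit B: ALT <5xULN (Section 11.3.3 and Table 13 title).
- Shared condition: chemistries normal, or no more than 1.5 times the participant's own baseline (all four places).
- Entry limit: ALT of 3xULN or more at Screening is exclusionary (Section 5.2, criterion 33). Participants with hepatitis C co-infection may enter if their liver enzymes meet entry criteria (criterion 20), so a baseline between 2 and 3xULN is permitted.

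**Step 1: where the limits alone differ.** An ALT from 3xULN to just under 5xULN fails A and meets B.

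**Step 2: apply the shared condition.** An ALT of 3xULN or more can satisfy it only if 1.5 × baseline ≥ 3xULN, that is, baseline ≥ 3/1.5 = 2xULN. The upper end of the disagreement is the participant's own 1.5 × baseline, up to limit B.

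**Step 3: put numbers in** (all in multiples of ULN).

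| Baseline ALT | 1.5 × baseline | ALT values where the texts disagree |
|---|---|---|
| 1.0 | 1.5 | none |
| 2.0 | 3.0 | only the single value 3.0 |
| 2.2 | 3.3 | 3.0 to 3.3 |
| 2.5 | 3.75 | 3.0 to 3.75 |
| just under 3.0 | just under 4.5 | 3.0 to just under 4.5 |

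Example: a participant with baseline 2.5xULN recovers to 3.5xULN, which is within 1.5 × 2.5 = 3.75xULN. Under Sections 5.5.1.3.2 and 7.4.5.6 the ALT condition is not met. Under Section 11.3.3 it is. At baseline 2.2xULN, an ALT of 4.0xULN exceeds 3.3xULN and fails every version, so there is no disagreement.

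**Step 4: baseline above the Screening limit.** Criterion 33 applies at Screening. Section 7.2.1 equates Baseline with Day 1, up to 35 days later, and chemistry is drawn again then. If Day 1 ALT had risen, 1.5 × baseline reaches 5xULN at a baseline of 5/1.5 = 3.33xULN. From there limit B caps the range, and the disagreement runs from 3xULN to just under 5xULN.

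**Step 5: look for a tie-break.** The cross-reference in Section 7.4.5.6 leads from limit A to limit B without comment. Section 5.5.1.3 makes a separate guideline binding but does not say which protocol figure it carries. Nothing shown resolves the conflict.

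**The case against.** The strongest reply is that the conflict is narrow and well guarded. Much of that stands.

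- Few participants will have a baseline ALT above 2xULN, meet a liver stopping criterion for a reason unrelated to study drug, and recover into the disputed range.
- Meeting either limit only allows the case to be considered. The Medical Monitor and the safety physician complete Table 13, senior physicians must agree, and the VSLC decides. Section 11.3.3 also asks for documented evidence of extensive drug resistance, which few participants are likely to have, since criterion 29 excludes known major integrase or NNRTI resistance mutations other than K103N.
- Section 7.4.4.2 separately requires Medical Monitor consultation before long-acting dosing continues at ALT of 3xULN or more, which covers the whole disputed range.
- The separate VSLC guideline may carry a single figure. Appendix 3 opens under a heading that calls its content VSLC guidelines.

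These points limit the consequences. They do not say which limit the people applying these gates should use.

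A reader might also infer more than the documents support:

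- **That everyone with ALT between 3 and 4.5xULN is treated differently.** The upper end is each participant's own 1.5 × baseline.
- **That the 5xULN limit can never operate.** This holds only if baseline ALT stayed below 3xULN.
- **That one text bars redosing and the other grants it.** Both govern consideration only.
- **That trial results are affected.** Under Section 9.3.1, stopping for an adverse event is not by that rule counted as HIV-1 RNA ≥50 c/mL. Any effect would fall mainly on the <50 c/mL endpoint, for very few participants, and is not shown to be material.

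**Conclusion.** The contradiction is real and stands in current protocol text: two ALT limits for one restart pathway, each stated twice, with a cross-reference from one to the other and no order of precedence shown. The texts differ for participants with baseline ALT above 2xULN whose ALT lies between 3xULN and 1.5 times their own baseline. They agree for any baseline below 2xULN.

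Two assumptions apply. The upper bound of 4.5xULN takes baseline ALT as <3xULN. In addition, the ALT limit in Sections 5.5.1.3.2 and 7.4.5.6 sits inside a bracket of examples, apparently because the bracket closes in the wrong place; it is read here as the intended criterion.

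The number affected is expected to be small and cannot be estimated from the protocol. The point rests on safety and clarity: a threshold for further long-acting dosing after a liver stopping event should have one value. It does not rest on any effect on the efficacy analyses.

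**What to change.** Reconcile Section 5.5.1.3.2, the restart text in Section 7.4.5.6, Section 11.3.3 and the Table 13 title to one ALT limit, chosen by the sponsor's hepatic safety experts. State it in one place and have the others refer to it. Check that the separately held VSLC guideline carries the same figure, and close the bracket of examples in Sections 5.5.1.3.2 and 7.4.5.6 before the criterion begins.

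The cost is a short protocol amendment, a corrected checklist and a check of the VSLC guideline. No analysis, sample size or data collection changes.
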